## **Immunogenicity assessments**

Assays for Anti-rhAnnexin V-128 IgG and IgM antibodies will be performed in serum samples by ELISA at screening visit (before test agent administration at the latest) at Day 30 (+/- 3 days) and at Day 56 (+/- 2 weeks), i.e. 2 weeks after second injection. An additional sample is required 3 months after the first administration of the 99mTc-rhAnnexin V-128 (Day 90 ± 14 days) in case of positive anti-annexin antibodies outcome in previous examinations.

For this purpose, 10 mL of blood will be collected per sample.

Serum will be prepared (following the same procedure as that used for PK samples – see Appendix 2), divided into six aliquots and frozen (-80°C) until complete decay. Three out of six serum samples per time-point will be then shipped to the local laboratory, where the analysis for anti-rhAnnexin V-128 antibodies will be performed (methods detailed in the Laboratory Manual).

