	
patients with AS, DAS28 Disease Activity Score assessments for patients with RA.
 

On Day 1, patients will have whole body scintigraphies with 99mTc-rhAnnexin V-128, vital signs assessment and an ECG. A pregnancy test will also be performed prior to rhAnnexin V-128 administration. The first 3 patients (who will not take part in the sub-study) will be imaged at 60 min and at 2 hrs after administration. Next enrolled patients will be imaged at a time in line with the results of the image acquisition in the first 3 patients who will have participated in the sub-study. Additional images, blood and urine samples will be taken for the 10 patients participating in the dosimetric and PK study.

At Day 2, patients will be called over the phone to inquire if they experienced allergic reactions such as edema or rash. Patients who will participate in the PK and dosimetric sub-study will be interviewed in face to face on site meeting during the visit on Day 2. For these last patients, blood/urine analysis, whole body scintigraphy with 99mTc-rhAnnexin V-128 will be repeated 24 hours later for the dosimetric and pharmacokinetics analyses. Vital signs and ECG will also be assessed.

At Day 30+- 3 days, all patients will have immunological evaluations as well as blood (haematology and biochemistry) and urine analysis, ECG and vital signs.

At 6 weeks (Day 42) ± 2 weeks, a whole body scintigraphy with 99mTc-rhAnnexin V-128 at a time in line with the results of the image acquisition in the first 3 patients who will have participated in the sub-study, ECG, physical examination, vital signs, blood/urine analyses, a pregnancy test for women with childbearing potential, BASDAI, BASFI, BASMI for patients with AS, DAS28 Disease Activity Score assessments for patients with RA will be performed in all patients.

At Day 43, patients will be called over the phone to inquire if they experienced allergic reactions such as edema or rash.

At 8 weeks (Day 56) ± 2 weeks, vital signs and immunological evaluation will be performed.

At Day 90+- 2 weeks, all patients will have immunological evaluations, ECG, physical examination and vital signs, blood and urine analysis, BASDAI, BASFI, BASMI for patients with AS, DAS28 Disease Activity Score assessments for patients with RA.

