Treatment	The single dose vial (rhAnnexin V-128: 0.40 mg) will be reconstituted with 740 MBq (20 mCi) of 99m Tc. The labelling reaction requires 90 minutes and the reconstituted radiolabelled product is stable for 6 h. For the purpose of this study, it is recommended to administer the reconstituted solution within 4 hours after completion of the labelling reaction. The drug is administered at a dose of 250 MBq as a single intravenous bolus over 10-20 seconds at Day 1 and at 6 weeks (42 days) +- 2 weeks after the first administration.
Inclusion/ exclusion criteria	
Inclusion criteria
 

Patients diagnosed with RA based on ACR/EULAR 2010 criteria with a score ≥ 6, OR Patients diagnosed with AS based on the ASAS criteria. Patients with RA must have serology assessment performed and documented at the time of enrolment.

Patient with RA active disease (DAS > 2,6) and the introduction of a Bi-DMARD treatment should be indicated. RA patients must at least be treated with DMARD (methotrexate,

[figure not shown]

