Pharmacokinetics	
whole body planar images at 30min, 60 min, 2hrs, 4 hrs and 24 hrs post-injection for the first 3 patients included in the sub-study. Depending upon the results in those 3 patients, the timeframe for dosimetry measurements and PK will be confirmed or modified with a time-point at 3 hrs (instead of 2 hrs) and 6 hrs (instead of 4 hrs) for the following 7 enrolled patients in the sub-study.
 
Radiation dose to the organ of interests (particularly the kidneys), effective dose equivalent and effective dose will be calculated following the MIRD committee guidelines using the OLINDA/EXM software.
 
Blood and urine collection and counting:
 
Venous blood samples will be drawn for each subject at screening, Day 30, Day 42 and Day 90 for lab analysis (Haematology, biochemistry).
 
For patients included into the subgroup of PK and dosimetric study, blood sample will also be collected for lab analysis (Haematology, biochemistry) at Day 2. For the first 3 patients, a further 10 ml of venous blood samples will be drawn at nominal times of 0, 5, 10, 15, 30, 60 minutes as well as 2 hrs, 4hrs and 24 hrs post administration. Depending upon the results in those 3 patients, the timeframe for dosimetry measurements and PK will be confirmed or modified with a time-point at 3 hrs (instead of 2 hrs) and 6 hrs (instead of 4 hrs) for the following 7 enrolled patients in the sub-study.
 
The following whole blood and serum aliquots will be prepared as described in Appendix 2, for radioactivity measurements, and PK.
 
For immunogenicity assays, venous blood samples will be drawn for each subject at screening, at Day 30 ± 3 days, at Day 56 ± 14 days and Day 90 ± 14 days.
 
Total quantity of collected blood samples for patients (participating or not in the PK and dosimetric sub-study) is described in Appendix 3.
 
Urine sample will be collected within 24 hrs prior to 99mTc-rhAnnexin V-128 administration, preferable just prior to its administration (0 h sample) to achieve bladder emptying. Urine collections will be obtained and volume recorded, possibly in the time intervals 0-1 h, 1 h – 4 hrs, 4 hrs -16 hrs, 16 hrs – 24 hrs post administration. Dual 2 mL aliquots of urine from each period will be counted in a gamma counter at local laboratory. Urine samples (10 mL) will also be analyzed by SEC-HPLC technique at local laboratory.
 
Blood clearance fractions and effective half-life estimates from multi-term non-compartmental exponential analysis will be calculated from serial measurements of radioactivity in the whole blood and serum.
 
Pharmacokinetic analysis will be also performed based on rhAnnexin V-128 serum concentration determined by ELISA method.
 
As mentioned above, venous blood samples of 10 ml volume each will be taken from the first 3 patients at nominal times of 0, 5, 10, 15, 30, 60 minutes as well as 2 hrs, 4hrs and 24 hrs post administration. Depending upon the results in those 3 patients, the timeframe for dosimetry measurements and PK samples will be confirmed or modified with a time-point at 3 hrs (instead of 2 hrs) and 6 hrs (instead of 4 hrs) for the following 7 enrolled patients in the sub-study. The blood will be processed and aliquoted as described in Appendix 2. Two aliquots of at least 0.6 mL of serum per time-point will be frozen at -80°C.

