**Visit schedule – Table 1**

Study Procedures	Screening ( $\pm 4$ weeks)	Day 1	24 hours 	Day 30 $\pm 3$ days	Day 42 $\pm 2$ weeks	Day 56 $\pm 2$ weeks	Day 90 $\pm 2$ weeks
Written informed consent	X						
Inclusion/exclusion criteria	X						
Medical history	X						
Concomitant medications including RA and AS treatment	X	X	X	X	X	X	X
Disease assessment (BASDAI, BASFI, BASMI for AS for AS patients, DAS28 scales including Ultrasound assessments for RA patients)	X				X		X
Physical examination	X				X		X
Vital signs (BP and HR)	X	X	X	X	X	X	X
Lab analysis (haematology, biochemistry; urine)	X		X	X	X		X
Venous/urine sampling (PK and dosimetry) 		X 	X				
Immunogenicity by ELISA 	X			X		X	X
Urine SEC-HPLC analysis 		X	X				
Pregnancy test	X	X			X		
Standard 12-lead ECG	X	X	X	X	X		X
rh-Annexin V-128 administration 		X			X		
Bone scintigraphy 	X						
Whole Body scintigraphic imaging 		X	X		X		
Adverse Events	X	X	X	X	X	X	X

 Only for patients participating to the dosimetric and PK substudies.

 Venous blood samples of 10 ml volume each will be taken from the first 3 patients at nominal times of 0, 5, 10, 15, 30, 60 minutes and 2 hrs, 4hrs and 24 hrs post administration as described in Appendix 2 for radioactivity measurements, and PK. Depending upon the results in those 3 patients, timeframe of radioactivity measurements and PK will be confirmed or modified with a time-point at 3 hrs (instead of 2 hrs) and 6 hrs (instead of 4 hrs) as required for the following 7 enrolled patients in the sub-study. The whole blood and serum samples (bullet points 1 and 2) will be counted in an auto-gamma counting system at the CHUV/NUC laboratory.

 Anti-rhAnnexin V-128 IgG and IgM antibodies will be performed in serum samples by ELISA. For this purpose 10mL blood samples will be collected at baseline, Day 30 ( $\pm 3$  days), Day 56 ( $\pm 2$  weeks) and Day 90 ( $\pm 2$  weeks) post administration of test agent (sample at 90 days is required only in case of positive anti-annexin antibodies outcome in previous examinations). Serum will be prepared, divided into six aliquots and frozen (-80°C) until complete decay. Three out of six serum samples per time-point will be then shipped to the central laboratory.

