#### **Study duration and End of Study**

Study duration is of 4 month +/- 2 weeks (including the screening period).

Eligible patients will receive two injections: one on Day 1 and a second administration 6 weeks +/- 2 weeks later. The end of the study is defined as the moment that the last enrolled patient has completed 18 days follow-up after completing the second 99mTc-rhAnnexin V-128 administration. An additional blood sample for immunological assay is required 3 months after the first administration of the 99mTc-rhAnnexin V-128 (Day 90 ± 14 days) in case of positive anti-Annexin antibodies outcome in previous examination.

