### **Study Medication Dose, Mode of Administration, Batch Number**

The "Kit for preparation of 99mTc-rhAnnexin V-128 for injection" consists of 1 patient dose.

The single dose vial (0.40 mg rh-Annexin V-128) will be reconstituted with 2 mL ± 0.2 mL containing 740 MBq ± 74 MBq (20 mCi ± 2 mCi) of 99mTc. The labelling reaction requires 90 minutes and the reconstituted radiolabelled product is stable for 6 h. For the purpose of this study, it is recommended to administer the reconstituted solution within 4 hours after completion of the labelling reaction,

Patients will receive 2 administrations of 99mTc-rhAnnexin V-128 , one on day 1 and one on day 42 (±14 days).

When investigational product is received at the site, the Investigator, Pharmacist or authorized designee shall check for accurate delivery and acknowledge receipt by signing and dating the documentation provided by the Sponsor and returning it to the Sponsor or designee. A copy of this documentation shall be retained for the Investigator file.

The dispensing of the investigational product shall be carefully recorded on an investigational product accountability form provided and an accurate accounting must be available for verification by the Clinical Research Associate at each monitoring visit.

Unused investigational product must not be discarded or used for any purpose other than the present study.

The Clinical Research Associate will periodically collect the Drug Accountability Forms and will check all investigational product (both unused and used) before making arrangements for authorizing their destruction at the investigational site.

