## **Laboratory Tests**

Laboratory tests (haematology, coagulation, blood chemistry and urinalysis) will be monitored before and during the study days mentioned in the study chart. A total volume of 100ml will be collected during the study. For each patient participating to the dosimetric and PK sub-study a total of 205 ml will be drawn throughout the study.

Descriptive statistics including shift tables will be generated for all laboratory tests performed i.e. the actual values and the changes from pre-injection by cross-tabulations (with classes for below, within, and above normal range).

Laboratory data will be analysed with respect to the normal ranges of values provided by the local laboratory and with respect to pre-defined levels of change in these values.

Abnormal laboratory test results will be tabulated.

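### The antibody sample meant for two weeks after the second injection has no minimum gap from it, and the documents conflict on whether antibody-negative patients are sampled again at Day 90

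*Protocol*

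**What the plan says.** **Second injection.** The Synopsis (Treatment) gives the injections "at Day 1 and at 6 weeks (42 days) +- 2 weeks after the first administration". Section 5 repeats this window.

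**Antibody sample after it.** Section 6, Immunogenicity assessments, takes the sample "at Day 56 (+/- 2 weeks), i.e. 2 weeks after second injection". The Synopsis, Table 1 and SAP 4.11 give Day 56 ± 2 weeks without the two-week clause. SAP 6.3 and 7.15 speak of 30 and 56 days post-administration and do not say which injection is meant.

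**A milestone that is counted from the second injection.** Section 3 ends the study when "the last enrolled patient has completed 18 days follow-up after completing the second" administration. This defines the end of the study and is not a sampling rule.

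**Day 90 for everyone.** The Synopsis (Study design and Methodology) says: "At Day 90+- 2 weeks, all patients will have immunological evaluations". Its blood-collection text says: "For immunogenicity assays, venous blood samples will be drawn for each subject at screening", and goes on to list Day 30, Day 56 and Day 90.

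**Day 90 only after a positive.** Table 1, footnote 3, says: "sample at 90 days is required only in case of positive anti-annexin antibodies outcome in previous examinations". The same condition appears in the Immunogenicity row of the Synopsis, Sections 3 and 6 of the protocol, and SAP 4.1, 4.11, 6.3 and 7.15.

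**Reporting.** SAP 7.15 promises a descriptive table. The only immunogenicity entry in SAP 10.1 is 14.3.6, a listing of reactive results by nominal visit. SAP 10.3 also lists immunogenicity samples, immunogenicity results, treatment administration and visit dates. Protocol Section 8 promises a separate PK/immunology analysis plan and report.

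**The concern.** A recombinant protein is given twice. The earlier human study of this product that the protocol describes gave a single dose to 12 volunteers and reported antibody results at 15 and 30 days. What this trial adds on immunogenicity is therefore the response to a second exposure. To call a patient negative after two doses, one needs a sample long enough after the second dose. The protocol's own choice is two weeks, but the windows do not secure it, and the one later sample that would do so may be withheld from exactly the patients who tested negative.

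Antibody response is a separate SAP endpoint (6.3), and the data monitoring committee reviews immunologic results. With 16 to 20 evaluable patients, one missed seroconversion moves the reported rate by 1/20 = 5.0 to 1/16 = 6.25 percentage points.

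**Working it through.** **Inputs**

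- Second injection: Day 42 ± 14, so Days 28 to 56 (Synopsis; Section 5). The phone call 24 hours after this injection is set at Day 43, which confirms that Day 42 is on the study-day scale.
- Day 56 sample: 56 ± 14, so Days 42 to 70 (Section 6; Table 1).
- Day 90 sample: 90 ± 14, so Days 76 to 104 (Table 1).
- Day 30 sample: 30 ± 3, so Days 27 to 33 (Table 1).

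**Plan's own figure.** At nominal dates the gap is 56 − 42 = 14 days, which reproduces the stated two weeks.

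**Gap = sample day − injection day, over the two windows**

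- Largest: 70 − 28 = 42 days.
- Smallest from the windows alone: 42 − 56 = −14 days.
- Smallest with the sample on a later day than the injection: 1 day. The permitted range in visit order is therefore 1 to 42 days.
- If ± 2 weeks is read instead as a tolerance around 14 days after the second injection: 14 ± 14 = 0 to 28 days, so there is still no useful minimum.

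**Illustrations (assumed visit patterns)**

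- Both visits shift by the same amount: the gap is always 14 days and no patient is affected.
- Sample kept at Day 56, second injection d days late: gap = 14 − d. With d = 7 the gap is 7 days; with d = 13 it is 1 day.

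**Day 90 sample after the second injection.** Smallest 76 − 56 = 20 days; largest 104 − 28 = 76 days. It is the only sample certain to reach 14 days.

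**Day 30 sample.** It can fall after an early second injection, by up to 33 − 28 = 5 days. Nominal visit therefore does not fully separate the two exposures.

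**Blood totals (Appendix 3; Section 8, Laboratory Tests)**

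- Outside the sub-study: 4 × 15 + 4 × 10 = 100 mL, which matches "A total volume of 100ml will be collected during the study". Without the Day 90 antibody draw it would be 90 mL.
- In the sub-study: 5 × 15 + 80 + 10 + 4 × 10 = 205 mL, or 195 mL without that draw.
- The totals are consistent with a Day 90 draw in everyone, but they could also be maximum volumes.

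**Number of patients.** SAP 4.2 expects at least 80% of 20 evaluable: 0.80 × 20 = 16, so about 16 to 20.

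**The case against.** The strongest reply is that the two-week clause in Section 6 already fixes the gap. Adding 14 days to the injection window gives 28 + 14 = Day 42 to 56 + 14 = Day 70, exactly the sample window. The ± 2 weeks may simply carry the injection window forward, with the gap meant to be 14 days throughout. This is a plausible reading and it limits the point: the 1 to 42 day range is what the windows permit if the clause is not enforced. But the clause appears only in Section 6, carries no tolerance of its own, and is absent from Table 1 and the SAP, so a site working from the visit schedule would not be held to it.

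On Day 90, one can say that Section 3 sends the reader to Section 6 and Table 1 for assessment details, and both make the sample conditional, so the all-patient text is a slip in the Synopsis. That may be so. The Synopsis contradicts itself, however, and if the conditional rule is the intended one, it is the rule that leaves negative patients without a later assay.

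It is also fair that immunogenicity is not a named protocol objective, that the documents give no seroconversion time, and that allergic symptoms are asked about 24 hours after each injection. Those calls do not replace serology.

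A reader might infer that the planned outputs would hide early sampling or a missing Day 90 assay. They would not: listings 16.2.4.15, 16.2.4.16, 16.2.5.1 and 16.2.5.2 cover all screened patients, and with so few patients the intervals can be worked out by hand. Nor can one say that immunology analysis is otherwise unplanned, since the promised PK/immunology plan may cover some of this.

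**Conclusion.** The point holds as a cheap improvement. The protocol intends a sample two weeks after the second injection, but its windows set no minimum gap and permit 1 to 42 days if visits stay in order and the two-week clause is not enforced. The Day 90 sample would close the gap, at 20 days or more after the second injection, but the documents disagree on whether antibody-negative patients have it. Under the conditional rule, a seroconversion after re-exposure can be missed and the patient counted as negative.

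The number affected is unknown. It is zero if the two visits always shifted together, and also zero if Day 90 was assayed in everyone. A reader might take the width of the permitted range, or a count of the date combinations inside it, as a measure of how often sampling was too early. Neither is: the documents give no visit dates. They also do not support saying that any seroconversion was in fact missed. The result rests on whole-day windows, the sample falling on a later day than the injection, and 14 days as the adequate interval, which is the protocol's own figure.

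**What to change.** **1. Sampling (protocol).** Time the sample at 14 days after the actual second injection, with a stated tolerance that stays clear of the Day 90 window. The target falls on Days 42 to 70 and the Day 90 window opens on Day 76, so at most 75 − 70 = 5 days late is available. A tolerance of 0/+5 days, as an example, gives Days 42 to 75 and a gap of 14 to 19 days. State in every place that the Day 90 sample is taken and assayed in all patients.

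This is too late for patients already sampled. Recruitment was to stop by the end of September 2017. Allowing up to 4 weeks of screening (assumption), Day 1 falls by 28 October 2017 and Day 70 by 5 January 2018, before the SAP date of 26 January 2018. For these patients, assay the Day 90 serum where it was drawn.

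**2. Reporting (SAP 7.15 table).** Summarise actual days since the most recent injection for all samples, reactive or not. Give positivity after injection 1 and after injection 2, each with the number of patients sampled in that period, assigned by actual dates. State how many patients have no assayed sample at least 14 days after injection 2. Align this with the separate PK/immunology plan.

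**Cost.** Part 1 is a protocol amendment plus at most about 20 ELISAs. The Synopsis already has all patients attend at Day 90, the draw is inside the 100 mL and 205 mL totals, and samples sent for ELISA may be kept for up to 10 years. Part 2 summarises dates already listed. The downsides are that fewer patients will count as assessed after injection 2, and that Day 90 serum may not exist for every negative patient.

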**Patients participating to the dosimetry and PK studies will undergo the following additional assessments:**

**Pharmacokinetics (blood and urine)**

Venous blood samples of 10 ml each will be taken just before administration of 99mTc-rhAnnexin V-128 and then at the following time-points: 5, 10, 15, 30, 60 min, 2 hrs, 4 hrs and 24 hrs post the first rhAnnexin V-128 administration for the first 3 patients included in the sub-study. Depending upon the results in those 3 patients, the timeframe for dosimetry measurements and PK will be confirmed or modified with a time-point at 3 hrs (instead of 2 hrs) and 6 hrs (instead of 4 hrs) for the following 7 enrolled patients in the sub-study. The following whole blood or serum aliquots will be prepared as described in Appendix 2:

- 1) 2 x 1 mL of whole blood will be used for radioactivity measurements
- 2) 2 x 1 mL of serum aliquots will also be used for radioactivity measurements
- 3) 2 x 0.6 mL at least of serum aliquots to be frozen at -80°C, will be used for pharmacokinetics measurements. After complete decay of radioactivity, one out of 2 aliquots/time-point will be shipped to the centralized laboratory and analyzed by ELISA to determine the rhAnnexin V-128 concentration in serum (See the Laboratory Manual for further instruction).

The whole blood and serum samples (bullet points 1 and 2) will be counted in a gamma counting system (CHUV/NUC laboratory) and compared to the count rate from a representative percentage of the injected activity inside the same counter.

Blood clearance fractions and effective half-life estimates from multi-term non-compartmental exponential analysis will be calculated from serial measurements of radioactivity in whole blood and serum. Pharmacokinetic analysis will be also performed based on rhAnnexin V-128 serum concentration determined by ELISA method.

Urine samples will be collected as follows (see also Appendix 2). One sample will be collected within 24 hrs prior to 99mTc-rhAnnexin V-128 administration, preferably just prior to the administration of study drug (0 h sample) to achieve bladder emptying. Quantitative urine collections will be obtained (and volume recorded) possibly in the time intervals 0-1 h, 1 h – 4 hrs, 4 hrs – 16 hrs, and 16 hrs – 24 hrs post administration. Dual 2 mL aliquots of urine from each period will be counted in a gamma counter at the CHUV/NUC laboratory. The mean between the two 99mTc radioactivity measurements and the measured volume of urine will be used to calculate the amount of 99mTc excreted in that period and the cumulative percent injected dose (radioactivity).

